17.2 Pharmacodynamic Summaries

17.2.1 Platelet Counts

Continuous descriptive statistics (as defined in Section 9.1.3) will be used to summarize the serum levels and changes from baseline (absolute values and percentages) by study part and treatment. Data from Part D will be summarized by planned and actual treatment (if the actual number of doses received differs from planned). CV will not be presented for changes from baseline summaries. If the total number of subjects per treatment is lower than 3 then the only descriptive statistics presented will be arithmetic mean, minimum and maximum

Linear plots of the arithmetic mean absolute values and changes from baseline (absolute and % change) by scheduled sampling time will be provided by part and treatment. For Part D these plots will be provided for both planned and actual treatment.

Linear plots of the combined individual serum levels (absolute values) and changes from baseline (absolute and % changes from baseline) by actual sampling time (spaghetti plots) will be provided by part and treatment. For Part D these plots will be provided for both planned and actual treatment.

Linear plots of the individual serum levels (absolute values) and changes from baseline (absolute and % changes from baseline) by actual time will be provided by subject.

All individual subject platelet counts and changes from baseline (absolute change and percentages) will be provided in the tables.

17.2.2 Platelet Parameters

Missing values in the calculation of any PD parameters will not be imputed and handled as missing values. The PD parameters for all subjects in the FAS set will be estimated from the platelet count-time profiles and platelet count change from baseline-time profiles (as specified in Table 2: PD Parameters). The calculation will be performed using the actual sampling times. If the actual time is missing, the scheduled time will be substituted in order to calculate the PD parameter.

Baseline is defined as the pre-dose sample of each period.

In calculation of AUC, the linear trapezoidal calculation method will be used. Descriptive statistics will be calculated and presented for all derived PD parameters by study part and treatment. In case of Part D by these data will be presented by planned and actual treatment (if the actual number of doses received differs from planned).

Individual PD parameters will be listed, and descriptive statistics will be summarized in tables.

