9.1.2 Imputation

Unless otherwise noted, data will not be imputed.

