9.1.3 Descriptive Statistics

Unless otherwise indicated, continuous variables will be summarized with the following descriptive statistics: n (number of observations), (arithmetic) mean, standard deviation (SD), minimum (min) value, median, and maximum (max) value. For PK and PD data, nblq (number of observations below the limit of quantification), CV, geometric mean, and coefficient of variation of the geometric mean (geoCV) will be presented additionally. If the total number of subjects per treatment is lower than 3 then the only descriptive statistics presented will be arithmetic mean, minimum and maximum.

Categorical data will be summarized with frequencies and percentages. Percentages by categories will be based on the number of subjects exposed within a treatment.

For categorical data the categories will be presented in the tables exactly as they appear in the eCRF / Database.

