17.1.2 Platelet Parameters

A therapeutic platelet count is defined as $\geq 50 \times 10^9$ /L and an increase from baseline of $\geq 20 \times 10^9$ /L (this will be referred to as threshold in Table 2: PD Parameters).

• Platelet parameters as defined in Table 2: PD Parameters

Table 2: Platelet PD Parameters calculated in WinNonLin.

Parameter	Description	Absolute values	Changes from baseline	% changes from baseline	SAS Programming Notes
t _{onset}	Time to onset of a therapeutic platelet count. Time that the response first crosses the threshold coming from the direction of the baseline value.	x			Tonset from WNL
R _{max}	Maximum platelet count following dosing, maximum and percentage platelet count change from baseline. Maximum observed response value.	x	x	x	Rmax from WNL
t _{max}	Time to maximum platelet count following dosing. Time of maximum observed response value.	X			Tmax from WNL
D _{aboveT}	Duration of a therapeutic platelet count. Total time that Response >= Threshold.	x			Time_Above_T from WNL
t _{offset}	Time greater than T _{onset} at which the curve first crosses back to the baseline side of threshold.	x			Toffset from WNL

AUC _{0-14d}	Area under the change from baseline platelet count-time curve for 14 days.	x	AUC0-14 from WNL
AUC _{0-28d}	Area under the change from baseline platelet count-time curve for 28 days.	X	AUC0-28 from WNL

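### Time to onset and offset of a therapeutic platelet count are summarised in responders only, so the onset row read alone can make a low-response treatment look as fast as a high-response one

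*SAP*

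**What the plan says.** SAP 17.1.2 defines a therapeutic platelet count as at least 50 × 10⁹/L together with a rise of at least 20 × 10⁹/L over baseline, and uses this as the threshold in Table 2. The first parameter in that table is "Time to onset of a therapeutic platelet count", defined as "Time that the response first crosses the threshold coming from the direction of the baseline value". The offset time is the first return below the threshold after onset, so it presupposes an onset. Protocol 8.7 also lists time to onset among the PD parameters.

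On handling, SAP 17.2.2 says "Missing values in the calculation of any PD parameters will not be imputed and handled as missing values", in line with the general rule in 9.1.2: "Unless otherwise noted, data will not be imputed". On analysis, 17.2.2 says "Descriptive statistics will be calculated and presented for all derived PD parameters by study part and treatment". Under 9.1.3 these statistics are "n (number of observations), (arithmetic) mean, standard deviation (SD), minimum (min) value, median, and maximum (max) value", with CV and geometric statistics added for PD data. When a treatment has fewer than 3 subjects, "the only descriptive statistics presented will be arithmetic mean, minimum and maximum"; n is not on that shorter list.

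SAP 9.5 lays out the Part B and C tables with an M254-period column, an IVIg-period column and a difference column. Neither document gives a time-to-event method, a censoring time or an assigned value for a patient who never reaches the threshold.

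**The concern.** A patient followed to the end of a period without reaching the threshold is not a patient with unknown data. The plan has observed that onset did not occur by the last count, which is a censored onset time. Treating it as missing removes from the onset summary exactly the patients in whom the drug did not work, and the number removed depends on the drug.

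Characterising the PD of M254 against IVIg is a primary objective of Part C, and the protocol presents a prompt platelet rise as a known feature of IVIg (section 2.1), so readers will look at the onset row. If response rates differ, that row compares different, outcome-selected sets of patients. It answers how fast responders respond, and it can easily be taken to answer how fast the drug works.

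**Working it through.** **1. What the plan produces.** The definition in 17.1.2 gives no onset value without a crossing. The no-imputation rules leave the value absent. The descriptive statistics use the values present. Each treatment column is therefore computed over that treatment's responders. SAP 9.5 does not define its difference column; read as a within-patient difference, it exists only for patients who respond on both drugs. One table row can then rest on three different patient sets.

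**2. Size, under an assumed onset law.** The documents give no time-to-onset figure to reproduce, so this step is an illustration. Assume onset among responders follows a gamma distribution with shape 2 and scale 1.2 days on both drugs, with distribution function F, and let π be the response rate.

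- Responders only: solve F(t) = 0.5. This gives t = 2.0 days, whatever π is.
- All patients, non-reachers censored at the end of follow-up: solve π·F(t) = 0.5.

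| π | F needed (0.5/π) | All-patient median | Responder-only median |
|---|---|---|---|
| 90% | 0.556 | 2.2 days | 2.0 days |
| 60% | 0.833 | 3.9 days | 2.0 days |
| 40% | 1.25, impossible | not reached | 2.0 days |

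**3. The same effect with 10 patients per treatment (assumed data).** Treatment X: 9 of 10 reach the threshold, at days 1, 1, 1, 2, 2, 2, 3, 4, 7. Treatment Y: 3 of 10, at days 1, 2, 3.

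- Responders only: medians 2.0 and 2.0 days; means 23/9 = 2.56 and 6/3 = 2.00 days. Y looks as fast or faster.
- All patients: median 2 days for X, not reached for Y.
- Response rates: 9/10 (exact 90% CI 61% to 99.5%) and 3/10 (9% to 61%).

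**4. Are unequal response rates plausible here?** The statistical output appended to the SAP (its section 4.1) gives model results for all subjects in Part C. As an input check on log maximum count, 4.0919 − 4.7980 = −0.7061, as printed. The 95% CI rebuilt as estimate ± t(0.975, 9.23) × 0.1172 is −0.9702 to −0.4420, against a printed −0.9702 to −0.4419.

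Assume normality on the log scale with the printed variances:

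- Reaching 50 × 10⁹/L: SD = √(0.1077 + 0.06513) = 0.416. IVIg: Φ((4.7980 − 3.912)/0.416) ≈ 98%. M254: Φ((4.0919 − 3.912)/0.416) ≈ 67%.
- Rising by 20 × 10⁹/L: SD = √(0.3740 + 0.1970) = 0.756. IVIg: Φ((4.4418 − 2.996)/0.756) ≈ 97%. M254: Φ((3.1437 − 2.996)/0.756) ≈ 58%.

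These are implied by the model and are not reported response rates. At 58% and 67%, the gamma law in step 2 gives all-patient medians of about 4.2 and 3.2 days.

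**5. How often the low-response treatment looks at least as fast.** This used 30,000 simulated trials, 10 patients per treatment and an assumed common onset law among responders (days 1, 2, 3, 4, 7 with probabilities 0.30, 0.30, 0.15, 0.10, 0.15), counting ties.

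| Response rates | By responder-only median | By all-patient median |
|---|---|---|
| 58% vs 97% | 64% | 27% |
| 30% vs 97% | 59% | 3% |

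At 58% vs 97% the underlying responder-only medians are 2 and 2 days, and the all-patient medians are 7 and 2 days.

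**The case against.** The strongest reply is that the plan already reports what the onset row leaves out. SAP 17.2.2.2 gives the overall response rate in Part C, defined by the same therapeutic count, with a 90% exact CI per treatment period on both the FAS and the PP set. Appendix 4 lists a response-rate table for Parts B, C and D. Individual PD parameters are listed, and n normally stands beside each summary. Part C plans 10 patients per cohort, so the fewer-than-3 exception should not apply to its treatment columns. All of this stands, and it means a careful reader can see the selection.

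The gap is narrower but remains. Part B plans 2 patients per cohort, where n is not among the statistics shown. If one of the two does not respond, the mean, minimum and maximum are all the other patient's value, and only the individual values reveal it.

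A reader might also infer more than the documents support:

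- That the SAP expressly drops non-responders. It does not. The quoted sentence in 17.2.2 can be read as covering missed platelet samples. The responder-only summary follows from the definition together with the absence of any other rule.
- That the plan conceals the difference in response, or breaks the within-patient comparison on which Part C rests. The mixed model in 17.2.2.1 covers maximum count, maximum change and AUC, not onset. No formal hypothesis testing is planned, and the difference in response is a planned secondary summary.
- That duration above threshold has the same defect. Table 2 defines it as total time at or above threshold, which is already zero for a patient who never gets there.
- That 90% against 40% is the expected contrast. It is the most extreme of the cases in step 2, and nothing in the documents points to 40%.

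**Conclusion.** The point holds as a minor one about presentation. Followed as written, the SAP yields onset and offset summaries over responders only, and within-patient differences only over patients who respond on both drugs. No primary or secondary conclusion rests on time to onset.

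Taken alone, the onset row can show 2.0 against 2.0 days where the all-patient medians are 2.2 days at 90% response, 3.9 at 60% and not reached at 40%. The onset distributions and response rates are assumptions. The masking itself needs only that response rates differ, and the appended model output makes that plausible. The documents contain no onset results, so nothing here shows that a reported onset comparison was misleading.

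**What to change.** In SAP 17.2.2:

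- Summarise time to onset over all FAS patients by Kaplan-Meier or cumulative incidence per treatment, censoring patients who never reach the threshold at their last platelet count in that period.
- Give the proportion with onset by fixed scheduled days, for example Days 2, 5, 8 and 15, all of which have a planned count in Part C.
- Show the number reaching the threshold out of N beside any responder-only onset or offset statistic, including when fewer than 3 subjects are summarised.

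This uses data already collected and costs some SAP wording and one extra table. With about 10 patients per treatment, the median will be imprecise and may not be estimable for a weak treatment; the fixed-day proportions still give a usable summary. Per-treatment curves do not restore a within-patient comparison of onset, and the text should not present them as doing so.

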17.2.2.1 Primary Statistical Analysis of Platelet Parameters

Efficacy analyses will be performed on Part C data using FAS. This is considered primary analysis. The ratio of effects between M254 and IVIg will be estimated from a linear mixed effect model on the natural

logarithms of absolute values R_{max} and change from baseline R_{max} , AUC₀₋₁₄ and AUC₀₋₂₈, with factors for baseline platelet count, sequence, subject nested within sequence, period and treatment. The factor of subject nested within sequence will be random effect and others are fixed effects. The estimated ratio will be obtained by exponentiation of the difference of least squares means in natural log-transformed parameters between M254 and IVIg. The ratios of geometric means and their 95% CIs will be presented. The same analysis will be performed for patients with baseline platelet level of $\leq 30 \text{ vs} \geq 30 \times 10^9/\text{ L}$ as exploratory analysis and only if there is sufficient number of patients in both groups. Otherwise the platelet baseline category and category covariate interaction term will be added to the model (as exploratory analysis).

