## 5.2 Eligibility Criteria for ITP Patients

## 5.2.1 Inclusion Criteria for ITP Patients (USA sites included)

Participants are eligible to be included in the study only if all of the following criteria apply:

- 1. Participant must be 18 years of age or greater at the time of signing the ICF.
- 2. Diagnosed with primary ITP (with or without splenectomy) according to the Hematology Guidelines for at least 3 months prior to screening.
- 3. Must have received at least 1 prior treatment for ITP NOTE: if received prior treatment with IVIg, and if known from medical history, must have responded as defined by an increase of platelet count above 50 × 10^9/L within 14 days of IVIg treatment.
- 4. Platelet count  $\geq$ 15 × 10^9/L and <50 × 10^9/L within 96 hours prior to start of study drug infusion on Day 1.
- 5. Body weight must be within a range that allows for the planned M254 infusion time to be completed in ≤4 hours. Please refer to the infusion rate schedule in the Infusion Manual and Section 6.1.1.1.M254
- 6. Maintenance immunosuppressive therapy, steroid therapy, cyclosporine A, mycophenolate mofetil, azathioprine, thrombopoietin receptor agonists, or danazol are allowed, but the dosages of all these medications must be stable for at least 4 weeks prior to Visit 1 (Day 1).
- 7. No history of clotting disorder other than ITP including no myocardial infarction within the last 6 months. No arrhythmia known to increase the risk of thrombotic events (eg, atrial fibrillation).
- 8. Male and females are eligible.
  - a. Male participants:
    - If male, surgically or biologically sterile. If not sterile, agreement to use an acceptable form of birth control with sexual partner (as described in Appendix 4) for 2 weeks prior to administration of study medication, during study treatment, and for 100 days following the last treatment (ie, study

Compound: M254 Protocol: MOM-M254-001

Protocol Date and Version:8 Global 28 April 2020

completion or premature discontinuation from the study), or abstain from sexual relations for the same duration.

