#### 9 STATISTICAL CONSIDERATIONS

#### 9.1 Sample Size Determination

The sample size has been chosen to provide adequate numbers of subjects and patients to characterize the safety, tolerability, PK, and PD of M254 and the study has not been formally powered.

No formal sample size calculation was performed for this study (Parts A, B, and D).

Part C is an exploratory study designed to obtain preliminary information on the safety and efficacy of M254 for the treatment of ITP.

Assuming ratio of M254 to IVIg in maximum change from baseline of platelet counts as **EG** 

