## 9.3.1 Efficacy Analyses

Endpoint	Statistical Analysis Methods
Primary	Efficacy analyses will be performed using Full Analysis Set (FAS). For Part C, for the ratio of effects between M254 and IVIg, a linear mixed effect model will be performed on the natural logarithms of maximum platelet counts, maximum change from baseline, and area under the curve (AUC), with factors for baseline platelet count, sequence, subject nested within sequence, period, and regimen. The factor of subject nested within sequence will be random effect and others are fixed effects. The estimated ratio will be obtained by exponentiation of the difference of least squares means in natural log-transformed parameters between M254 and IVIg.
Secondary	Overall platelet response rate and its 90% exact binomial confidence interval in each treatment period will be presented. Duration of a clinically significant platelet response will be presented descriptively.
Exploratory	Will be described in the statistical analysis plan finalized before database lock.

Protocol Date and Version:8 Global 28 April 2020

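### SAP 17.2.2.1 calls the ratio of absolute maximum platelet counts a ratio of effects, but it contains the pre-dose count in both arms and is compressed toward 1; no lead parameter is named

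*SAP*

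**What the plan says.** SAP 17.2.2.1 defines the primary Part C platelet analysis: "The ratio of effects between M254 and IVIg will be estimated from a linear mixed effect model". The model is fitted to the logs of absolute Rmax, change-from-baseline Rmax, AUC0-14 and AUC0-28. Baseline count, sequence, period and treatment are fixed effects, and subject within sequence is random. SAP Table 2 defines Rmax as the largest observed value and puts both AUCs on the change from baseline. SAP 17.2.2 adds: "Baseline is defined as the pre-dose sample of each period".

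On back-transformation and reporting, SAP 17.2.2.1 says "The estimated ratio will be obtained by exponentiation of the difference of least squares means" and "The ratios of geometric means and their 95% CIs will be presented". No parameter is ranked first.

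Protocol 9.3.1 has the same structure: for the ratio of effects, the model "will be performed on the natural logarithms of maximum platelet counts, maximum change from baseline, and area under the curve". Protocol 9.1 contains a planning sentence that begins "Assuming ratio of M254 to IVIg in maximum change from baseline of platelet counts as"; the value and what follows are redacted. No hypothesis is tested (Protocol 3.5, SAP 9.4.3).

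**The concern.** A ratio of effects should compare what the two treatments added. Absolute Rmax is the pre-dose count plus the rise, so its ratio compares pre-dose count plus M254 rise with pre-dose count plus IVIg rise. ITP patients enter with counts from 15 to just under 50 × 10^9/L (Protocol 5.2.1, criterion 4), which is not negligible beside the rise expected from IVIg.

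Because nothing is tested, the estimated ratios and their intervals are the primary pharmacodynamic result of Part C. The plan puts two quite different numbers for peak response under one description, in one planned table (Table 14.2.2.1.3), without saying which is the effect of M254 relative to IVIg. If M254 is weaker than IVIg, quoting the absolute version overstates its relative effect. If M254 is stronger, it understates it.

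**Working it through.** **Inputs.** These are the all-subjects results in section 4.1 of the statistical output appended to the SAP. Log scale, M254 minus IVIg; 21 of 21 observations used for both Rmax parameters.

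| Parameter | LS mean IVIg | LS mean M254 | Difference | SE | df |
|---|---|---|---|---|---|
| Absolute Rmax | 4.7980 | 4.0919 | −0.7061 | 0.1172 | 9.23 |
| Change-from-baseline Rmax | 4.4418 | 3.1437 | −1.2981 | 0.2049 | 9.02 |

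**Step 1: reproduce the reported figures.** 4.0919 − 4.7980 = −0.7061. Estimate ± t(0.975, df) × SE gives −0.9702 to −0.4420 (reported −0.9702 to −0.4419). The same calculation for change from baseline gives −1.7615 to −0.8347 (reported −1.7614 to −0.8348). Differences are rounding.

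**Step 2: exponentiate.**
- Absolute Rmax: exp(−0.7061) = 0.494, 95% CI 0.379 to 0.643. Geometric means: IVIg 121.3, M254 59.9.
- Change-from-baseline Rmax: exp(−1.2981) = 0.273, 95% CI 0.172 to 0.434. Geometric means: IVIg 84.9, M254 23.2.
- The change-from-baseline AUCs agree with the second figure: AUC0-14 exp(−1.4084) = 0.245; AUC0-28 exp(−1.5289) = 0.217.
- Baseline ≤30 subgroup (11 observations): exp(−0.6844) = 0.504 absolute, exp(−1.1790) = 0.308 change from baseline.

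**Step 3: does the pre-dose count explain the gap?** The implied baseline is 121.3 − 84.9 = 36.4 for IVIg and 59.9 − 23.2 = 36.7 for M254, so about 36.5. Then (36.5 + 23.2)/(36.5 + 84.9) = 59.7/121.4 = 0.49, which recovers the absolute ratio. Subtracting geometric means is approximate, but the agreement is close.

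**Step 4: size over the entry range.** Let B be the pre-dose count, G the IVIg rise and f the true ratio of rises. The absolute ratio is (B + f·G)/(B + G). With G = 84.9:
- f = 0: 15/99.9 = 0.15 at B = 15; 30/114.9 = 0.26 at B = 30; 49/133.9 = 0.37 at B = 49.
- f = 0.50: 57.45/99.9 = 0.58 at B = 15; 72.45/114.9 = 0.63 at B = 30; 87.45/129.9 = 0.67 at B = 45.

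**Step 5: does the covariate help?** Adjustment compares the arms at a common B, but that B stays in both geometric means. A simulation of the crossover model with the baseline covariate (20 patients, 150 replicates) confirms this. It assumed baseline uniform on 15 to 50, median IVIg rise 85, log-SD of the rise 0.5 between and 0.25 within subjects, and no measurement noise in the maximum.

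| True ratio of rises | Absolute Rmax ratio | Change-from-baseline ratio |
|---|---|---|
| 0 | 0.26 | not estimable |
| 0.10 | 0.34 | 0.10 |
| 0.273 | 0.47 | 0.27 |
| 0.50 | 0.64 | 0.50 |
| 1.0 | 1.00 | 1.00 |
| 1.5 | 1.35 | 1.50 |

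**The case against.** The strongest reply is that nothing is missing. Three of the four planned ratios are already on change from baseline, and the appended output labels the two Rmax parameters separately. SAP 17.2.2.1 also describes the results as ratios of geometric means, which is accurate. Part C is exploratory, no margin or success rule attaches to any ratio, and both intervals lie well below 1, so the direction of the conclusion does not change. Absolute count is a legitimate measure: Protocol 8.7 lists it, and the therapeutic threshold uses it. It also always has a logarithm. All of this stands. It limits the point to labelling and precedence, but it does not turn a ratio of peak counts into a ratio of effects or say which figure leads.

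Four stronger readings are tempting, and the documents do not support them.
- A reader might infer that the parameter was chosen to flatter M254. The compression works both ways, and the protocol's rationale expected M254 to be many times more potent than IVIg; on that expectation absolute Rmax would understate it.
- A reader might infer that an inert M254 would correctly read 0 on the change-from-baseline scale. The log of a change of 0 or less is undefined. Such observations would drop out, or noise in repeated counts would make the maximum change positive.
- A reader might take the inert-drug reading at a baseline near 50 to be about 0.4. That comes from holding the IVIg maximum at 121 while baseline varies, which shrinks the assumed IVIg rise. Holding the rise at 84.9 gives the figures in Step 4.
- A reader might take Protocol 9.1 as proof that change-from-baseline Rmax was meant to take precedence. The sentence is cut off by redaction, and SAP 6.1 says no formal calculation was made for Part C. It is supporting evidence only.

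**Conclusion.** The point holds as one of labelling and precedence. The absolute-Rmax ratio is not a ratio of effects, and the baseline covariate does not make it one. In the sponsor's own output the choice of parameter moves the stated M254:IVIg figure from 27% to 49%, and each point estimate lies outside the other's 95% interval. The absolute version also looks more precise on the log scale (SE 0.117 against 0.205), consistent with the added pre-dose count damping variation in the rises.

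The 0.49 and 0.27 are direct from the output. The Step 4 ranges assume an IVIg rise of 84.9 and the same pre-dose count in both periods. The simulated values rest on the distributions stated with them, and measurement noise in the maximum would raise the inert-drug figure further. The validity of the planned change-from-baseline ratios is not in question, apart from the missing rule for non-positive values.

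**What to change.** In SAP 17.2.2.1:
- Name change-from-baseline Rmax as the lead parameter for the ratio of effects, with AUC0-14 and AUC0-28 supportive. This matches the scale visible in Protocol 9.1. It also kept all 21 observations, whereas AUC0-14 used 19 and AUC0-28 used 17.
- State in advance a rule for non-positive change-from-baseline values that does not silently drop non-responders. Options are a stated floor value with a sensitivity analysis, or a baseline-adjusted difference on the original scale. The appended methods text (section 2) records that the SAP had no rule for negative AUCs and that they were left out.
- Keep absolute Rmax, labelled 'ratio of maximum counts (includes baseline)'.

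SAP 3.0 says the SAP supersedes the protocol's statistical considerations, so the difference from Protocol 9.3.1 can be recorded in SAP 7.1. The cost is SAP wording, table labels and a small extra analysis for the non-positive rule. The headline M254:IVIg figure becomes less favourable, with a wider log-scale interval.
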